**16 Study visits**

Study visits were scheduled at enrolment; at 1, 4, 12, and 24 weeks after treatment; and then every 12 weeks until the end of the study or if there was any specific need after enrolment. Body weight, height, heart rate, blood pressure, blood glucose, full blood count, liver function tests, renal function and ECG were obtained during protocol visits and in-between periods if needed. All adverse events, which were identified by the investigators as at least possibly treatment-related during the 24-week treatment phase, were collected by the investigator. At each visit, the drug will be handed over to the parent/guardian in an amount sufficient to last the interim duration.

## 17 Treatment

### 17.1 Standard case management

| Arms                                 | Assigned Interventions  |
|--------------------------------------|---|
| Active
Comparator:
Propranolol | 
Drug: Propranolol
 
Initiated at a dosage of 1 mg/kg per day divided 3 times daily for 1 week and then increased to 2 mg/kg per day divided 3 times daily from week 2.
 
2 mg/kg per day in 3 doses from week 2 after a gradual increase in the dose in the first week.
 
Other Name: None
 |
| Active
Comparator:
Atenolol    | 
Drug: Atenolol
 
Initiated at a dosage of 0.5 mg/kg per day in a single dose for 1 week and then increased to 1 mg/kg per day in a single dose from week 2.
 
1 mg/kg per day in a single dose from week 2 after a gradual increase in the dose in the first week
 
Other Name: None
       |

In the propranolol group, propranolol was initiated at a dosage of 1.0 mg/kg per day divided 3 times daily for 1 week and then increased to 2 mg/kg per day divided 3 times daily from week 2. The treatment schedule was at least 6 months.

In the atenolol group, atenolol was initiated at a dosage of 0.5 mg/kg per day in a single dose for 1 week and then increased to 1 mg/kg per day in a single dose from week 2. The treatment schedule was at least 6 months.

Patients were administered the first dose of  $\beta$ -blocker at 8:00 am. During  $\beta$ -blocker treatments, the dose was adjusted for weight gain. At the end of treatment, the drug dose was adjusted according to the tapering schedule, which was determined by investigators and was supposed to be 4 weeks.

#### Tapering schedules of drug discontinuance

| Week | Propranolol | Atenolol |
|------|-------------|----------|
|------|-------------|----------|

---

|   |   |                                      |
|---|---|--------------------------------------|
| 1 | 1.5 mg/kg per day divided 3 times daily | 0.75 mg/kg per day in a single dose  |
| 2 | 1.0 mg/kg per day divided 3 times daily | 0.5 mg/kg per day in a single dose   |
| 3 | 0.5 mg/kg per day divided 3 times daily | 0.25 mg/kg per day in a single dose  |
| 4 | 2.5 mg/kg per day divided 3 times daily | 0.125 mg/kg per day in a single dose |
| 5 | Discontinued                            | Discontinued                         |

---

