### ***21.3 Collection and management of adverse events***

The frequency of adverse events (e.g., sleep disturbance, cool or mottled extremities, diarrhea, etc.) were collected by the investigator and reported by parents. The investigators collected any untoward medical occurrence in the form of signs, symptoms, abnormal laboratory findings, or diseases that emerged or worsened relative to baseline assessment. All adverse events that were identified by the investigators as at least possibly treatment-related (treatment-emergent adverse events or adverse events that have worsened since baseline) were included in the analysis. For each adverse event, the percentage of subjects who experienced at least 1

---

occurrence of the given event was summarized by treatment group. Adverse events during the initial 24-week treatment phase were compared between the two groups.

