**22 Tapering and discontinuation of treatment**

Propranolol or atenolol were tapered and stopped at an appropriate time, which was primarily based on the response and lesion regression after treatment. In this trial, the treatment was tapered and discontinued on complete or nearly complete resolution of IH or if no further improvement of IH (for 12 weeks of observation) was observed after month 6. At the end of the treatment period, the drug dose was gradually reduced over 4 weeks and then cease. For more detail regarding the procedures for tapering and discontinuation of treatment, refer to the **Treatment** section.

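### The propranolol taper table prints 2.5 mg/kg per day for week 4: five times the week-3 dose, above the full treatment dose, and contrary to the planned gradual reduction

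*Combined protocol and SAP*

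**What the plan says.** Section 17.1 sets the maintenance dose in each arm. Propranolol starts at 1 mg/kg per day and is "then increased to 2 mg/kg per day divided 3 times daily from week 2". Atenolol starts at 0.5 mg/kg per day and is "then increased to 1 mg/kg per day in a single dose from week 2". Both are given for at least 6 months.

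The tapering table that follows gives the weekly propranolol doses as:

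- week 1: "1.5 mg/kg per day divided 3 times daily"
- week 2: "1.0 mg/kg per day divided 3 times daily"
- week 3: "0.5 mg/kg per day divided 3 times daily"
- week 4: "2.5 mg/kg per day divided 3 times daily"
- week 5: stopped

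The atenolol column reads 0.75, 0.5, 0.25 and 0.125 mg/kg per day, then stopped.

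Section 22 describes the intent in words: "At the end of the treatment period, the drug dose was gradually reduced over 4 weeks and then cease". For the detail it sends the reader back to the Treatment section, where this table sits. No other part of the document corrects or explains the week-4 entry.

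**The concern.** A taper has to go down, and the last propranolol step goes up. A site that followed the table as printed would give an infant the highest propranolol dose of the whole trial for one week and then stop it outright. Section 5 names hypoglycemia and bronchial hyperreactivity as rare propranolol effects that can be life-threatening.

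Three features of the plan add to the hazard.

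- **Supervision.** The planned doubling from 1 to 2 mg/kg per day in week 1 comes with 8 hours of in-house monitoring (Section 21.1). No monitoring is specified for the taper. After week 24, visits are 12 weeks apart and drug is supplied to cover the interval (Section 16), so a four-week taper can run entirely at home.
- **Detection.** Under Section 21.3, "Adverse events during the initial 24-week treatment phase were compared between the two groups". Section 16 ties adverse event collection to the 24-week treatment phase, and Section 21.6 defines serious events within the 6 months of treatment. The taper follows at least 6 months of treatment, so harm from it would fall outside the between-arm comparison.
- **Asymmetry.** Only the propranolol arm has the faulty entry. Rebound (Section 20.5) is assessed after week 24 in patients who have stopped or are tapering. If the printed dose were given, the arms would come off treatment in different ways and the rebound comparison would be confounded, in a direction that cannot be predicted.

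**Working it through.** **Inputs.** Full doses are from Section 17.1: propranolol 2 and atenolol 1 mg/kg per day. Weekly taper doses are from the tapering table.

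**Formulas.** Share of full dose = taper dose / full dose. Ratio = propranolol dose / atenolol dose.

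| Stage | Propranolol (mg/kg/day) | Share of full | Atenolol (mg/kg/day) | Share of full | Ratio |
|---|---|---|---|---|---|
| Full dose | 2.0 | 100% | 1.0 | 100% | 2.0 |
| Taper week 1 | 1.5 | 75% | 0.75 | 75% | 2.0 |
| Taper week 2 | 1.0 | 50% | 0.5 | 50% | 2.0 |
| Taper week 3 | 0.5 | 25% | 0.25 | 25% | 2.0 |
| Taper week 4 | 2.5 | 125% | 0.125 | 12.5% | 20.0 |

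**Size of the discrepancy.**

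- Week 4 against week 3: 2.5 / 0.5 = 5.0.
- Week 4 against full dose: 2.5 / 2.0 = 1.25.
- Per single dose, at three a day: 2.5 / 3 = 0.833 mg/kg, against 0.5 / 3 = 0.167 mg/kg in week 3.

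**Can any rule in the table produce 2.5?**

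- Keeping the 2:1 ratio: 2 × 0.125 = 0.25.
- Halving week 3, as atenolol does (0.25 to 0.125): 0.5 / 2 = 0.25.
- Continuing the constant 0.5 step of weeks 1 to 3: 0.5 − 0.5 = 0.

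None gives 2.5. Two independent routes give 0.25, which is 0.25 / 2.0 = 12.5% of full dose, the same share as atenolol in week 4, or 0.25 / 3 = 0.083 mg/kg per single dose. Against that value the printed entry is 2.5 / 0.25 = 10 times too high.

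**Other propranolol doses in the protocol.** None exceeds 2 mg/kg per day. Re-treatment of significant rebound (Section 17.2) also uses 2, so the printed week-4 dose has no counterpart elsewhere.

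**Patients potentially exposed.** Section 12 plans 180 per arm and assumes 20% dropout. The ceiling is 180. If all the assumed dropout came before the taper, about 180 × 0.80 = 144 would reach it. Either number applies only if every site followed the table literally.

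**The case against.** The strongest reply is that this is a visible decimal slip and not a dosing decision. The row sits in a table headed as a taper, the figure exceeds the treatment dose, and the neighbouring column makes the intended value easy to infer. Section 17.1 also says investigators determined the taper, so a clinician would probably have questioned the entry. Nothing in the documents shows that any child received 2.5 mg/kg per day. All of this is fair, and it is why the point concerns a faulty instruction and makes no claim of harm done. It does not make the printed dose right, and investigator discretion is a weak safeguard when this is the only week-by-week schedule given.

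Some consequences do need conditions attached. Exposure of up to 180 patients is a ceiling. Distortion of the rebound comparison depends on the printed dose having been given, and its size is unknown. Late harm need not go unseen altogether: Section 21.2 asks parents to report events at any time, and Section 16 continues 12-weekly visits with heart rate, blood pressure, glucose and ECG. What stands is the narrower point that such harm would not enter the between-arm comparison. The limited adverse event window is also a general feature of the plan and does not arise from this table.

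Two further points have some force. The parent booklet is described in Section 21.2 as a place to record adverse events, so it may carry no dosing text. And because much of the protocol is written in the past tense, a notice to sites may come after the tapers are finished. That makes the check of dispensing records more important.

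A misreading of the table when the text was extracted cannot be wholly excluded. The other entries are coherent, and a look at the source page would settle it.

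**Conclusion.** The concern holds and must be fixed. The week-4 propranolol entry is wrong as written: 5.0 times week 3, 125% of full dose, and in direct conflict with Section 22. The table's own pattern indicates 0.25 mg/kg per day, which would make the printed figure a tenfold error. That value is an inference and needs clinical confirmation.

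The rating rests on patient safety, since this is a live dosing instruction for infants. Sample size, alpha, power and the week-24 primary endpoint are untouched because the taper follows at least 6 months of treatment. Among the outcomes, rebound is the one plainly at risk, and only if the printed dose was dispensed.

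**What to change.** 1. The responsible clinicians and pharmacy confirm the intended week-4 propranolol dose. The candidate to put to them is 0.25 mg/kg per day in three divided doses.
2. Correct the cell so that the table agrees with Sections 17.1 and 22, and correct anything that was copied from it, such as dispensing instructions, and the parent booklet if it carries doses.
3. Notify all six sites in writing.
4. Check dispensing records for every propranolol patient who reached the taper. If any were supplied at 2.5 mg/kg per day, review their safety data through the taper and after stopping, report them, and repeat the rebound comparison without them as a sensitivity analysis.

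The cost is a one-line protocol correction, a notice to sites and a records check. No analysis needs to change unless the records show that the printed dose was used.

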### ***17.2 Rebound management***

Significant rebound after stopping the medication was treated by reinstitution of daily therapy with either propranolol (2 mg/kg per day) or atenolol (1 mg/kg per day) until hemangioma remission.

### ***17.3 Other co-interventions***

In both arms, oral antibiotics (cefaclor suspension), topical ointment antibiotics (mupirocin) and/or wound dressings were permitted to treat ulcerated IH and were recorded. The requirement for any additional IH-specific intervention was considered treatment failure.

## **18 Collection and assessment of series of digital photographs**

Digital photographs of each target hemangioma were acquired by the site investigators at baseline and at 1, 4, 12, 24 and 96 weeks after treatment. The detailed procedures are listed below:

(1) The investigators used a unified camera model. The acquisition procedures ensured consistency in lighting, exposure and distance from the camera. All digital photographs were obtained using digital single-lens reflex cameras (Nikon D7000 or Nikon D7100, Nikon Inc., Melville, NY).

(2) For each participant site, the series images were taken in the same room. The room was a naturally well-lit room. The acquisition of digital photographs was performed carefully to avoid glare and direct light deep into the room.

(3) The background behind the patient when the images are acquired was either the parent's (or guardian's) chest or shoulder or an examination couch. The parents and patients wore light-color, nonreflective clothes. Similarly, the examination couch was covered with a light blue, non-reflective bed sheet.

(4) For each patient, at least one photograph (a front-on view with or without side-on view) was taken at each visit. If the patient had a mixed hemangioma, front-on view and side-on view photographs were taken (not mandatory).

(5) The quality of all the photographs was verified by site investigators before they were transferred to the CIS. If the photographs were not compliant with the acquisition protocol, repeated acquisition of the images was immediately performed.

(6) Each photograph was uploaded with the following information: patient ID number and date of photograph acquisition. The central investigators assessed the quality of the digital photograph once more.

(7) Digital photographs were independently assessed by three investigators (research assistants) working in the CIS who were unknown to the study group assignment and blinded to the clinical information. None of these investigators was involved in the clinical management of patients with IH. They were trained specifically to assess hemangioma evolution (response or nonresponse), hemangioma size and hemangioma color using a series of digital photographs.

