**10 Eligibility/Inclusion criteria:**

|                             |                               |
|-----------------------------|-------------------------------|
| Ages Eligible for Study:    | Between 5 and 20 weeks of age |
| Sexes Eligible for Study:   | Both                          |
| Accepts Healthy Volunteers: | No                            |

Presenting an infantile hemangioma with the following characteristics:

- (1) Superficial or mixed IHs.
- (2) Proliferating hemangioma lesions impairing function (including vision, eating and hearing), in cosmetically sensitive regions, or with ulceration and/or bleeding.
- (3) The minimum diameter of the lesion was 1.5 cm on the face and 3 cm outside the face (or 1.5 cm if it was ulcerated).
- (4) Consent of parents (or the person with parental authority in families): signed and dated written informed consent.

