-Deep, which was defined as blue and located below the skin surface (deep lesions were not considered target hemangiomas in this study); or

-Mixed, which was defined as having both superficial and deep components.

Investigators at all sites received standardized training on hemangioma assessments, including training in measurement techniques and the classification of hemangiomas.

(7) Treatment indications included:

-Disfigurement: Segmental IH; Head or facial IH  $\geq 1.5$  cm; Neck, truck or extremity IH  $\geq 3.0$  cm.

-Causing functional disturbance: Periocular IH with threat to vision, nasal tip and lip ( $\geq 1.5$  cm). If functional concerns were documented, indication for treatment was not classified as disfigurement (facial IH  $\geq 1.5$  cm).

-Ulceration (IH  $\geq 1.5$  cm): ulcerated IH appearing anywhere on the body surface.

-Bleeding (IH  $\geq 1.5$  cm): Bleeding IH appearing anywhere on the body surface.

---

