## 19 Primary outcome measures

The primary outcome measure was the clinical response at 6 months in the intention-to-treat population. The intention-to-treat population was defined as all patients who had undergone randomization. If after assignment, a patient did not receive a drug administration or if an evaluation was never made after drug administration, the patient was excluded from the intention-to-treat population.

Digital photographs of IHs were independently obtained by three investigators who were unknown to the study group assignment. In the case of multiple IHs, only the most clinically important IH (typically the largest or most ulcerated IH) was documented.

Changes in IH size and color were classified as a complete response, nearly complete response, partial response or no response. The primary outcome measure was any response or nonresponse at 6 months in the intention-to-treat population of all patients who underwent randomization. The any response included compete, nearly complete and good responses; the nonresponse included stable or deteriorated:

-A complete response was defined as no redundant tissue or telangiectasia was identified.

-A nearly complete response was defined as a minimal degree of telangiectasis, erythema and skin thickening.

-A partial response was defined as a size reduction or change in color that did not meet the nearly complete resolution criteria.

-Stable was defined as no changes in size or color between baseline and month 6.

-Deterioration was defined as further growth of the target hemangioma.

Treatment failure was defined as patients withdrawing from trial treatment due to nonresponse and/or severe adverse events.

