**W24**

**W24**

## 20 Secondary outcome measures

### 20.1 Hemangioma Activity Score

The key secondary outcome measure was the Hemangioma Activity Score (HAS), which was measured at baseline and at 1, 4, 12 and 24 weeks using digital photographs. The photographs of the target hemangioma acquired at each visit were sent to the CIS. The consecutive digital photographs were assessed by centralized evaluation at West China Hospital of Sichuan University. Three trained investigators who were unknown to the study group assignments independently evaluated the digital photographs taken at baseline and the follow-up visits. According to previous reports, changes in an individual HAS could be used to evaluate the effect of treatment. Baseline scores were subtracted from posttreatment scores to obtain the change in HAS or the decrease in hemangioma proliferative activity after treatment.

The HAS system has three scoring forms, including the degree of deep swelling, the color of the hemangioma, and the ulceration assessment:

(1) Assessment of the degree of swelling (or protrusion or elevation). A proliferating superficial or mixed IH can present as a protrusion with an overlying red tint. If there is visible swelling (or protrusion or elevation), it was scored as follows:

-Six points if the swelling (or protrusion or elevation) was tense;

-Four points if the swelling (or protrusion or elevation) was 'neutral' (i.e., not tense or less tense) at baseline or had <50% reduction at follow-up;

-Two points when the swelling (or protrusion or elevation) was reduced by 50% or more at follow-up; or

-Zero points when there was no more visible swelling (or protrusion or elevation) at a follow-up.

If the patient had superficial IH and showed no visible evidence of swelling (or protrusion or elevation) at baseline, this step was omitted or we set the point as 0. However, the score for no swelling (which was zero) affected the final score.

(2) Assessment of the color of the IH. The hemangioma color was assessed by blinded central investigators. A bright-red (or shining-red) color suggested that the hemangioma was very actively proliferating. A diminishing red color on the surface was seen during the phases of involution. It is therefore possible that different scores might have been applied to different phases of the same hemangioma. A bright-red hemangioma received the highest score.

---

The intensities of hemangioma color were rated from 5 through 0:

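### The side-on photograph is optional for mixed hemangiomas and views need not match across visits, which adds avoidable reading error to HAS, week-1 response and week-96 response, and a narrower risk to the primary endpoint

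*Combined protocol and SAP*

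**What the plan says.** **Which views are required.** Section 18 schedules photographs at baseline and weeks 1, 4, 12, 24 and 96. The general minimum in item (4) is that "at least one photograph (a front-on view with or without side-on view) was taken at each visit". For mixed lesions it adds: "If the patient had a mixed hemangioma, front-on view and side-on view photographs were taken (not mandatory"). No sentence asks for the same set of views at successive visits.

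**Quality checks.** Under item (5) the site checks each image: "If the photographs were not compliant with the acquisition protocol, repeated acquisition of the images was immediately performed". Item (6) adds a central check after upload. A missing side view breaches nothing in the acquisition rules, so neither check is bound to catch it.

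**Who reads the images.** Under item (7), three trained central readers work independently and are "unknown to the study group assignment and blinded to the clinical information".

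**What they must judge.**
- Section 19, primary outcome: "Changes in IH size and color were classified as a complete response, nearly complete response, partial response or no response". Partial response needs only shrinkage or a colour change. Deterioration is further growth. Complete and nearly complete response are defined partly by the absence of redundant tissue and by minimal skin thickening.
- Section 20.1, HAS: swelling is scored 6, 4, 2 or 0 from photographs. One category reads: "Two points when the swelling (or protrusion or elevation) was reduced by 50% or more at follow-up".
- Section 20.2: successful initial response is any fall in HAS at week 1.
- Section 20.6: complete or nearly complete response at week 96, read from photographs.

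**Which lesions are eligible.** Section 10 admits "Superficial or mixed IHs". Section 15 defines the second type: "Mixed, which was defined as having both superficial and deep components".

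**The concern.** A front-on photograph shows outline and colour well and height poorly. Mixed lesions have a deep part by definition, and the HAS swelling item grades height. Item (4) lets an infant have a profile view at baseline and none at week 24, or have one at one site when a similar infant at another site does not. The reader must then judge a 50% reduction in protrusion from images that may not show protrusion comparably, and has no clinical record to fall back on.

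At stake are HAS, which Section 20.1 names as the key secondary outcome, the week-1 result derived from it, and the week-96 result, which turns on residual tissue. The primary endpoint is exposed less, through deep growth that goes unseen beneath a fading surface.

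**Working it through.** **1. Does another section close the gap?** The tape measurement of lesion size in Section 15 is a pretreatment site measurement. Section 16 does not list lesion size among the visit measurements, and no section supplies a size measurement to the readers. The gap stays open.

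**2. HAS.** Section 20.1 divides the total by the number of items scored and then adds ulcer points. With swelling S and one colour item C, the score before ulcer points is (S + C)/2.

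| Swelling misread | Shift, one colour item | Shift, two colour items |
|---|---|---|
| 4 read as 2 | 2/2 = 1.0 | 2/3 = 0.67 |
| 2 read as 0 | 2/2 = 1.0 | 2/3 = 0.67 |
| 4 read as 0 | 4/2 = 2.0 | 4/3 = 1.33 |

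The plan gives the scale as 0 to 8. These are errors in a single reading, not shifts in a group mean.

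**3. Week-1 response.** Take S = 4 and C = 5 at both baseline and week 1. The score is (4 + 5)/2 = 4.5 each time, so there is no initial response. Read week-1 swelling as 2 and the score is (2 + 5)/2 = 3.5, which counts as success. One misread step changes the binary result.

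**4. Week 96.** Colour change alone cannot satisfy the complete or nearly complete categories, because both also concern tissue bulk. Residual bulk that is not seen can therefore change the class.

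**5. Primary endpoint.** Three cases, under the Section 19 definitions:
- Fades, bulk unchanged: partial response by definition. A side view changes nothing.
- Fades, grows in depth: meets the colour criterion for partial response and also the definition of deterioration. Section 19 gives no precedence. Without a profile view the growth may not be seen at all.
- Does not fade, grows in depth: nonresponse whether it is read as stable or as deteriorated.

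Only the second case is a route to a false response.

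**6. Noninferiority, illustration only.** The plan states no figure for misreading, so there is nothing to reproduce. Assume a share m of lesions is mixed, and that a true nonresponder with a mixed lesion is read as a responder with probability f, equal in both arms. With k = m × f, each response rate p becomes p + (1 − p)k, so the gap d becomes d(1 − k).

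Take 80% for propranolol and 65% for atenolol, a true gap at the −15% margin of Section 12. Assume 150 evaluable per arm (180/1.2) and a one-sided 2.5% test, reading the two-sided 0.05 that way. The chance of declaring noninferiority is Φ[(d(1 − k) + 0.15)/SE − 1.960], where SE is the square root of the summed p(1 − p) of the two arms divided by 150.

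| m | f | k | Apparent rates | Apparent gap | Type I error |
|---|---|---|---|---|---|
| – | 0 | 0 | 80.0% v 65.0% | −15.0 | 2.5% |
| 0.3 | 0.1 | 0.03 | 80.6% v 66.1% | −14.6 | 3.1% |
| 0.5 | 0.2 | 0.10 | 82.0% v 68.5% | −13.5 | 4.9% |
| 0.7 | 0.4 | 0.28 | 85.6% v 74.8% | −10.8 | 15.0% |

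For the third row, SE = √[(0.82 × 0.18 + 0.685 × 0.315)/150] = 0.0492, and Φ(0.015/0.0492 − 1.960) = 4.9%. The documents give neither m nor f, so the table shows a direction and a range, not an estimate.

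**The case against.** The strongest reply concerns the primary endpoint. A reader might infer that optional side views let surface fading pass wrongly as response and so bias the noninferiority result toward atenolol. The documents do not support that. Fading without loss of bulk is a partial response by the plan's own definition, and better photographs would not alter it. What remains is a subset of mixed lesions: those that fade, grow in depth and lack an adequate profile view. For that subset f is probably well below the larger values in the table. A reader who saw the growth would still lack a rule for classing it. This objection stands and confines the primary-endpoint point.

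A reader might also infer that swelling cannot be scored at all. That goes too far. Item (4) says both views were taken for mixed lesions before relaxing the requirement, which suggests usual practice with tolerance for a missed view. How often one was missed is unknown. Section 18 also standardizes camera, room, lighting and distance, has two quality checks, and uses three trained readers. These measures improve each image but do not guarantee a profile view or matched views.

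The HAS shifts above are for single readings with no known frequency. Part of the difficulty, telling tense from neutral swelling in a photograph, may persist with a side view. Both points are fair. They limit the claimed size but do not remove the avoidable part of the error.

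**Conclusion.** The point holds as a measurement weakness that is cheap to remove. It falls mainly on the HAS swelling item, the week-1 response and the week-96 response. A one-step swelling error moves an individual HAS by 1.0 with one colour item scored, and missing residual swelling entirely moves it by 1.0 to 2.0. This rests on two judgements: that a front-on view shows height poorly, and that some visits lack a side view. The documents do not say how many.

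For the primary endpoint the risk is limited to unseen growth in depth under a fading surface. Equal misreading of nonresponders would shrink a true gap and so favour a noninferiority conclusion, but the documents do not allow its size to be estimated. No bias in the primary result is shown.

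**What to change.** - **Section 18 item (4):** strike the parenthetical that makes the views for mixed lesions optional. For mixed lesions, and for superficial lesions with visible elevation at baseline, require front-on and side-on views, matched in side and framing, at baseline and weeks 1, 4, 12, 24 and 96.
- **Item (5):** make a missing side view a reason for immediate retake at the site.
- **Item (6):** have the central check flag a missing side view and count it by arm and visit. This check follows upload, so a retake at the same visit may no longer be possible.
- **Section 19:** state how a lesion that fades but grows is classed.
- **Images already taken:** report missing side views by arm, site and visit. Reader agreement on the swelling item would be a useful addition.

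Cost: one more photograph at an existing session with the same camera and readers, about a minute of visit time, occasional retakes and protocol wording. The sample size does not change.
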